### Safety Assessments

Safety assessments will include the following through End of Study for each Group:

- Physical examinations
- Vital sign measurements
- Clinical laboratory parameters (hematology, serum chemistry, urinalysis and CD4+ T-cell count)
- Monitoring of AEs and concomitant medications
- Anti-Trogarzo® antibody levels (immunogenicity of Trogarzo®)

Laboratory samples will be collected every two weeks, at visits where Trogarzo® is administered. Beginning at Day 29 (4 weeks), non-laboratory safety assessments will be performed weekly through Day 99 (14 weeks) for the Sentinel Group and Core HIV-uninfected Group, and through Day 85 (12 weeks) for the Core HIV-infected Group.

## **2.2. Study Objectives**

### **2.2.1. Primary**

The primary objectives of this study are to:

- Evaluate the safety of Trogarzo® administered as an undiluted IV push over 30 seconds in clinically-stable human immunodeficiency virus type-1 (HIV-1) infected subjects with at least 3 months of stable treatment with a Trogarzo®-containing antiretroviral (ARV) regimen or healthy HIV-uninfected volunteers
- Compare the AUC and trough serum drug concentration after IV infusion with the diluted drug to the AUC and trough concentration after IV push with the undiluted drug

### **2.2.2. Secondary**

The secondary objectives of this study are to:

- Assess HIV-1 viral load for IV Infusion compared to IV push in HIV-1 infected subjects only.
- Characterize noted HIV-1 sensitivity/susceptibility changes in participants with an increase in plasma viral load to levels above 1,000 copies/mL on two consecutive measurements at least 2 weeks apart in HIV-1 infected subjects only.
- Determine the presence and significance of anti-Trogarzo® antibodies, if any (immunogenicity of Trogarzo®)

## **2.3. Study Drug Dosage and Administration**

The study drug, Trogarzo®, is a humanized IgG4 monoclonal antibody (MAb) approved for use in treatment-experienced patients in combination with other ARV agents for the treatment of multi-drug resistant HIV-1 infection and is administered via IV.

Maintenance doses of 800 mg Trogarzo® will be administered to all study subjects every two weeks throughout their participation in the study.

The Day1/Baseline and Day 15 doses will be administered as diluted IVs (IV Infusion - 800 mg in 250mL normal saline; 3.2 mg/mL) over 15 minutes in accordance with Trogarzo® prescribing information. Subsequent Trogarzo® doses on study will be administered at increased concentration over a shorter interval (< 15 minutes – see Study Design for more detail).

All patients will continue on all other ARV medications as prescribed by the primary care provider throughout study participation. Any changes in ARV treatment will be recorded with reasons for treatment modification. All patients will return to routine Trogarzo® administration via IV Infusion over 15 minutes in accordance with the prescribing information after completing participation in the study.

#### **2.4. Procedures**

##### **2.4.1. Subject Identification**

Once consent is obtained and study eligibility has been determined, a subject will be enrolled into the study and will be assigned a Participant Identification (PID) number. The 5-digit PID number will consist of a 2-digit site number and a 3-digit sequential subject number.

##### **2.4.2. Randomization**

This will be an open-label, non-randomized study.

##### **2.4.3. Blinding/Unblinding**

There will be no blinding/unblinding considerations for this open-label, non-randomized study.

##### **2.4.4. Replacement**

If a subject in the study is discontinued due to any reason other than safety as detailed in Section 4.3 (Safety Monitoring and Toxicity Management Plan) of the study protocol, another subject may be enrolled to replace the lost subject to achieve a total of 20 subjects successfully completing participation in the study.

Study participants who:

1. miss 2 consecutive visits or
2. have more than one treatment visit out of window or
3. have 3 non-treatment visits over 4 weeks that are out of window will be discontinued from the study and replaced.

### **3. Statistical Analysis Considerations**

#### **3.1. Sample Size**

Anticipated enrollment is 20 subjects from approximately 7 to 8 sites in the United States.

### **3.2. Analysis Populations**

#### **3.2.1. Intent-to-Treat (ITT) Population**

The ITT population is defined as all subjects enrolled into the study. Subject disposition will be based on the ITT population. The ITT Analysis Set will be used for the AUC and trough serum drug concentration and the secondary effectiveness analysis (assessment of the HIV-1 viral loads).

#### **3.2.2. Safety (SAF) Population**

All subjects who receive at least one partial dose of study drug will be included in the SAF Population. Subjects will be analyzed according to the treatment (dose regimen) they actually received. The SAF Population will be used for the safety analyses.

### **3.3. Data Handling**

#### **3.3.1. Measurement Times**

The nominal visit time point entered on the electronic case report forms (eCRFs) will be used. Subjects are asked to adhere to the following visit schedule:

##### **Sentinel Group**

- Study drug administration visits with safety assessments take place every two weeks beginning at Day 1/Baseline and continuing through Day 99 (14 weeks).
- Sentinel Group subjects will be asked to return for the final study assessments indicated for the EOS and Follow-up visits at Days 99 (14 weeks) and 113 (16 weeks), respectively. Subjects who are discontinued or who withdraw from the study prematurely are also requested to complete the assessments for these two study visits. (Refer to the Schedule of Events tables in the protocol for details on procedures for each scheduled study visit and for PK sampling time points.)

##### **Core HIV-infected Group**

- Study drug administration visits with safety assessments will take place once every two weeks beginning at Day 1/Baseline and continuing through Day 85 (12 weeks).
- Core HIV-infected Group subjects will be asked to return for the final study assessments indicated for the EOS and Follow-up visits at Days 85 (12 weeks) and 99 (14 weeks), respectively. Subjects who are discontinued or who withdraw from the study prematurely are also requested to complete the assessments for these two study visits. (Refer to the Schedule of Events tables in the protocol for details on procedures for each scheduled study visit and for PK sampling time points.)

##### **Core HIV-uninfected Group**

- Study drug administration visits with safety assessments will take place once every two weeks beginning at Day 1/Baseline and continuing through Day 71 (10 weeks).
- Core HIV-uninfected Group subjects will be asked to return for the final study assessments indicated for the EOS/Days 99 visit (14 weeks). Subjects who are discontinued or who withdraw from the study prematurely are also requested to complete the assessments for these two study visits. (Refer to the Schedule of Events tables in the protocol for details on procedures for each scheduled study visit and for PK sampling time points.)

### **3.3.2. Clinical Laboratory Data Handling Conventions**

If a subject has multiple results in the clinical laboratory data for the Screening visit, only the last result prior to the first dose of study drug will be included in the analysis. If a subject has multiple results (retests) for subsequent visits, the retest results will only be included in the analysis if the subject does not have a value recorded for the original assessment at the given visit.

### **3.3.3. Baseline Values**

Baseline is defined as the last assessment prior to the first dose of study drug (Day 1 for all HIV infected subjects, Day -55 for HIV uninfected subjects).

### **3.3.4. Missing Data Conventions**

Subjects with missing data at Day 1/Baseline will use the Screening visit value as their Day 1/Baseline result. Unless otherwise specified, missing data for subsequent visits will be considered missing at random and will not be imputed. If necessary, imputation of partial dates may be performed during the data analysis and will be documented (e.g., missing month=July; missing day=15).

## **3.4. Statistical Methods**

### **3.4.1. General Overview and Plan of Analysis**

The data collected are intended primarily for clinical review and interpretation. The analysis of study data will be primarily descriptive, with emphasis on tabular and graphical displays. Descriptive statistics will be used to guide decisions as to the clinical relevance of findings. Unless otherwise stated, p-values will be determined only if they appear to be warranted from the summary statistics.

Where applicable, summaries will be displayed in the following subject groupings:

- 1) Sentinel Group;

- 2) Core HIV-infected Group;
- Core HIV-uninfected Group and
- 3) Total.

In addition, the safety and efficacy summaries will present results for each of the dosing methods (IV push over 30 seconds, Infusion or Bolus over 10, 5, and 1 minute, and all IV infusions over 15 minutes).

For continuous data, descriptive statistics will be presented as number of subjects (n), mean, standard deviation, median, minimum, and maximum. For categorical data, the frequency and percentage of subjects in each category will be presented. Percentages will be based on non-missing data unless otherwise specified.

Data collected during this study will be assigned to the appropriate Analysis Phase, Analysis Period, and Analysis Subperiod (where applicable) in which it occurred. The assignment will be based on the visit date, or in the case of cumulative data such as AEs and concomitant procedures, based on the start date. Tables, listings, and graphs will reflect the assignments. A complete description of the phases, periods, and subperiods for the Sentinel and Core groups can be found in Appendix 1.

Data will be described and analyzed using the SAS System Version 9 (SAS Institute Inc., Cary, NC, SAS System). Individual subject data will be presented in subject data listings.

## **4. Statistical Analysis**

### ***4.1. Subject Disposition***

The number of subjects in the ITT and SAF Populations will be tabulated.

Study completion data will be summarized for all enrolled subjects. The number and percent of subjects who complete treatment; discontinue study medication prematurely; or discontinue the study prematurely will be tabulated. The primary reason for premature discontinuation of study medication and/or discontinuation from study participation will be tabulated. Any additional reason(s) for premature discontinuation of study medication will also be tabulated. A listing of all enrolled subjects will be provided.

### ***4.2. Demographic and Physical Characteristics***

Summary statistics will be presented for demographic and other Baseline characteristics for the ITT Population. Tabulations for age, sex, ethnicity (Hispanic/Latino, Not Hispanic or Latino, Unknown), and race (American Indian/Alaska Native, Asian, Black/African American, Native Hawaiian/Other Pacific Islander, White, Unknown, or Other) will be

presented. Age (years) will be calculated as the integer part of [(date of screening - date of birth + 1)/365.25]. Baseline physical characteristics, such as height (cm) and weight (kg), will also be summarized.

A listing of demographic and Baseline characteristics will be presented, as well as a listing of medical history.

#### ***4.3. Analysis of Safety and Tolerability***

Safety and tolerability will be assessed by both clinical and laboratory examinations. Summary statistics will be presented by AEs; hematology and serum chemistry; vital signs, (changes from Baseline and clinically significant findings); and abnormal physical examination findings in the SAF Population. Clinical laboratory values outside the normal ranges will be flagged in subject data listings. Non-numeric data will be presented in subject data listings, but will not be summarized.

##### **4.3.1. Extent of Study Drug Exposure**

Summary statistics will be presented for the cumulative dose (mg) and duration of treatment received by the subjects in the SAF Population. Duration of treatment will be represented as number of days from first dose of study drug. Corresponding listings will also be generated for study drug administration.

##### **4.3.2. AEs**

All AEs will be coded using MedDRA dictionary version 22.0. The use of another version will not be considered a violation of the SAP, nor require an amendment to the plan. All summary tables will be based on coded preferred terms (PTs), instead of verbatim terms. The categories and definitions of severity and causal relationship for all AEs, including the criteria for which an AE is to be classified as “serious,” are as described in the protocol (Section 8).

A treatment-emergent AE (TEAE) is defined as any event not present before exposure to study drug or any event already present that worsens in either intensity or frequency following exposure to study drug. All AEs entered on the Adverse Events eCRF will be analyzed as TEAEs. A TEAE with missing severity or relationship will be considered severe or related, respectively.

The overall incidence of TEAEs will be summarized for all subjects in the SAF Population. The number and percentage of subjects having the following will be tabulated:

- TEAE
- Serious TEAE
- TEAE leading to discontinuation
- TEAE with outcome of death

- TEAE related to study drug (definitely, probably, or possibly)
- Severe TEAE
- Class C TEAE per the Centers for Disease Control and Prevention (CDC) Classification System for HIV Infection

The overall incidence of TEAEs will also be summarized by System Organ Class (SOC), and by SOC and PT. The number and percentage of subjects reporting an event, as well as the number of events reported by the subjects will be tabulated. The incidence of serious TEAEs and TEAEs leading to study discontinuation (if any) will be summarized in the same manner. If there are multiple occurrences of the same TEAE within any SOC or PT for the same subject, only the first occurrence will be counted.

The incidence of TEAEs by severity/grade (mild, moderate, severe, or potentially life-threatening) and by relationship to study drug (unrelated, possibly related, probably related, and definitely related), and the incidence of serious AEs (SAEs) by relationship to study drug, will also be summarized.

All other AEs will be classified as non-TEAEs and identified in listings only. Serious TEAEs, TEAEs leading to study discontinuation, and TEAEs with an outcome of death will be presented in separate listings, if needed.

#### **4.3.3. Clinical Laboratory Parameters**

Summary statistics will be presented for laboratory measurements overall for all subjects in the SAF Population. Urinalysis results will be presented in a listing only. The following analytes will be tabulated/listed:

- **Hematology:** complete white blood cell count with differential, hemoglobin, hematocrit, and platelets.
- **Serum chemistry profile:** albumin, alkaline phosphatase, alanine aminotransferase (ALT), amylase, aspartate aminotransferase (AST), blood urea nitrogen, calcium, chloride, creatine phosphokinase, creatinine, direct bilirubin, gamma glutamyl transferase, glucose, lactate dehydrogenase, magnesium, phosphorus, potassium, sodium, total bilirubin, total protein, and uric acid. In addition, eGFR will be presented using the following formula:  $eGFR = 1.86 \times [Creatinine/88.4]^{-1.154} \times [Age]^{-0.203} \times [0.742 \text{ if female}] \times [1.210 \text{ if Black}]$ .
- **CD4+ Cell Counts**

Urinalysis results will be presented in a data listing and will include results from microscopic testing only. Pregnancy test, Serum Follicle-Stimulating Hormone (FSH) test, Hepatitis Serology, C-reactive Protein, and Viral Resistance Testing will also be presented in a data listing only.

Normal ranges for the laboratory parameters will be provided by the laboratory that performed the assessments. All normal ranges will be standardized and results will be reported in standard units. The tables will include summary statistics for the assessments and the changes from Baseline to each subsequent time point of measurement. A listing of subjects with abnormal (i.e., outside normal range) laboratory assessments will also be presented.

Potentially Clinically Significant (PCS) criteria may be applied to laboratory parameters as clinically indicated, and if applied, will be summarized as described above. PCS is defined as a laboratory value that is lower or higher than a laboratory's normal range limits.

Note: Electronic clinical laboratory data will be received at Westat. Data reconciliation will be performed to resolve any discrepancies with the Oracle database. Details of data receipt will be described in the Data Receipt Plan.

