Each AE should be recorded to represent a single diagnosis. Accompanying signs (including abnormal laboratory values) or symptoms should NOT be recorded as additional AEs. If a diagnosis is unknown, sign(s) or symptom(s) should be recorded as an AE(s). Changes in laboratory values are only considered to be AEs if they are judged to be clinically significant (i.e., if some action or intervention is required or if the investigator judges the change to be beyond the range of normal physiological fluctuation). If abnormal laboratory values findings are the result of pathology for which there is an overall diagnosis (e.g., increased creatinine in renal failure), the diagnosis only should be recorded as an AE.

Pre-planned procedures (surgeries or therapies) that were scheduled prior to the start of AE collection are not considered AEs. However, if a pre-planned procedure is performed early (e.g., as an emergency) due to a worsening of the preexisting condition, the worsening of the condition should be captured as an AE. Elective procedures performed where there is no change in the subject's medical condition should not be recorded as AEs but should be documented in the subject's source documents.

Medical Dictionary for Regulatory Activities (MedDRA) and World Health Organization Drug Dictionary (WHODD) will be used to code all AEs and classify all medicines, respectively. All coding will be performed by Westat and reviewed and approved by the medical monitor.

All AEs, whether serious or not, should be followed to a satisfactory resolution or until the Investigator deems the event to be chronic or the subject to be stable and the AE is determined to be not clinically significant.

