#### **4.3.3. Clinical Laboratory Parameters**

Summary statistics will be presented for laboratory measurements overall for all subjects in the SAF Population. The following analytes will be tabulated/listed:

- **Hematology:** complete white blood cell count with differential, hemoglobin, hematocrit, and platelets.

- **Serum chemistry profile:** albumin, alkaline phosphatase, alanine aminotransferase (ALT), amylase, aspartate aminotransferase (AST), blood urea nitrogen, calcium, chloride, creatine phosphokinase, creatinine, direct bilirubin, gamma glutamyl transferase, glucose, lactate dehydrogenase magnesium, phosphorus, potassium, sodium, total bilirubin, total protein, and uric acid. In addition, eGFR will be presented using the following formula:  $eGFR = 1.86 \times [Creatinine/88.4]^{-1.154} \times [Age]^{-0.203} \times [0.742 \text{ if female}] \times [1.210 \text{ if Black}]$ .
- **CD4+ Cell Counts**

Urinalysis results will be presented in a data listing and will include results from microscopic testing only. Pregnancy test, Serum Follicle-Stimulating Hormone (FSH) test, Hepatitis Serology, C-reactive Protein, Prothrombin Time and Partial Thromboplastin Time, and Viral Resistance Testing will also be presented in data listings only.

Normal ranges for the laboratory parameters will be provided by the laboratory that performed the assessments. All normal ranges will be standardized and results will be reported in standard units. The tables will include summary statistics for the assessments and the changes from Baseline to each subsequent time point of measurement. A table of subjects with abnormal (i.e., outside normal range) laboratory assessments will also be presented as a frequency of the incidence of each DAIDS toxicity grade (1 – 4) and route of administration.

Potentially Clinically Significant (PCS) criteria may be applied to laboratory parameters as clinically indicated, and if applied, will be summarized as described above. PCS is defined as a laboratory value that is lower or higher than a laboratory's normal range limits.

Note: Electronic clinical laboratory data will be received at Westat. Data reconciliation will be performed to resolve any discrepancies with the Oracle database. Details of data receipt will be described in the Data Receipt Plan.

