**Listing 16.2.7.1.1**  
**Clinical Laboratory Test**  
**Hematology**

Group	Subject ID	Visit	Date of Sample (Study Day)	Period[1]	Test	Result (L/H) [2]	Unit	Lower Limit of Normal	Upper Limit of Normal	Potentially Clinically Significant[3]	
Sentinel	302-XX-XXX XXXXXXXXXX	2016-03-04 (-172)	XXXXXXX	Basophils	0	10  /L	0	0.2			
					Basophils/Total Cells	0	%	0	2		
				Eosinophils	0.02	10  /L	0	0.57			
					Eosinophils/Total Cells	1	%	0	6.8		
				Hematocrit	0.31 (L)	Proportion of 1	0.39	0.54	YES		
	302-XX-XXX XXXXXXXXXX	2016-11-14 (84)	XXXXXXX		Hemoglobin	106 (L)	g/L	127	181	YES	
					Leukocytes	1.62 (L)	10  /L	3.8	10.7	YES	
					Lymphocytes	0.6 (L)	10  /L	0.91	4.28	YES	
					Lymphocytes/Total Cells	37	%	15.4	48.5		
					Monocytes	0.16	10  /L	0.12	0.92		
Core HIV-infected	302-XX-XXX XXXXXXXXXX	2016-11-14 (84)	XXXXXXX	Monocytes/Total Cells	10	%	2.6	10.1			
					Neutrophils	0.84 (L)	10  /L	1.96	7.23	YES	
					Neutrophils/Total Cells	52	%	40.5	75		
					Platelets	278	10  /L	140	400		
Core HIV-uninfected	302-XX-XXX XXXXXXXXXX	2016-11-14 (84)	XXXXXXX	Basophils	0.08	10  /L	0	0.2			
					Basophils/Total Cells	2.3 (H)	%	0	2	YES	
					Eosinophils	0.19	10  /L	0	0.57		
					Eosinophils/Total Cells	5.5	%	0	6.8		
					Hematocrit	0.39	Proportion of 1	0.39	0.54		
Core HIV-uninfected	302-XX-XXX XXXXXXXXXX	2016-11-14 (84)	XXXXXXX	Basophils	0.08	10  /L	0	0.2			
					Basophils/Total Cells	2.3 (H)	%	0	2	YES	
					Eosinophils	0.19	10  /L	0	0.57		
					Eosinophils/Total Cells	5.5	%	0	6.8		

[1] Period represents the timeframe when the visit took place. NOTE - Since labs are assessed pre-dose, the value of PERIOD in the lab listings will be previous to the value of PERIOD in listings for post-dose assessments.

[2] L = Below lower limit of normal; H = Above upper limit of normal.

[3] Potentially Clinically Significant is defined as having a result either below the lower limit of normal or above the upper limit of normal.

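### The IV push SAP grades no laboratory output by DAIDS toxicity, and its potentially clinically significant flag only repeats the out-of-range flag

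*SAP*

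**What the plan says.** Two SAPs cover the study, one for the IV push portion (Sentinel and Core Groups) and one for the IM portion.

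- **Push SAP, 4.3.3.** The rule is that "PCS is defined as a laboratory value that is lower or higher than a" given laboratory's normal limits. Its use is optional: "Potentially Clinically Significant (PCS) criteria may be applied to laboratory parameters as clinically indicated, and if applied, will be summarized as described above". For abnormal results the plan is that "A listing of subjects with abnormal (i.e., outside normal range) laboratory assessments will also be presented".
- **Push mock listings.** The hematology, chemistry and other-laboratory listings all have a PCS column. The hematology footnote reads "Potentially Clinically Significant is defined as having a result either below the lower limit of normal or above the upper limit of normal". The abnormal-results listing (16.2.7.1.5) shows value, unit, limits and a low/high mark, but no grade.
- **Push mock tables.** The laboratory tables give by-visit summaries and change from baseline. The table list contains no graded or shift table.
- **IM SAP, 4.3.3.** The PCS definition is the same, but abnormal results are also "presented as a frequency of the incidence of each DAIDS toxicity grade (1 – 4) and route of administration" (Tables 14.3.2.1 and 14.3.2.2).
- **Protocol.** Section 4.3 builds the dose-limiting toxicity definition on Grade 3 or greater and requires Grade 3 and 4 laboratory results to be confirmed by repeat. Section 7.2.1 has such results, CD4+ excepted, repeated within 72 hours and discussed with the medical monitor or Sponsor. Section 8.3 states: "Changes in laboratory values are only considered to be AEs if they are judged to be clinically significant".

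**The concern.** The safety of the 30-second push is a primary objective (Protocol 2.1). The protocol uses toxicity grade to decide which laboratory results need action, but the push analysis plan never tabulates or lists laboratory results by grade. The one label that sounds like a severity screen, PCS, is triggered by any departure from the normal range, so a trivial deviation and a marked one receive the same mark.

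The two ways a Grade 3-4 laboratory result can be counted in a push table both rest partly on investigator judgement, either of clinical significance or of drug relationship. The study is open-label with no concurrent control. A count by grade and dosing method is the one display that would not depend on that judgement, and it is missing for the push.

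**Working it through.** **Step 1. Where a Grade 3-4 laboratory result can appear in the push outputs**

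| Output | What it shows | Condition |
|---|---|---|
| TEAE tables by severity (14.3.1.3.1 to 14.3.1.3.3) and the Severe TEAE row (14.3.1.1.1 to 14.3.1.1.3) | Counts by grade and period | Investigator reports the change as an AE |
| Table 14.1.2, reasons for discontinuation | Count | Confirmed, considered drug related, and led to discontinuation |
| Hematology and chemistry tables | N, mean (SD), median, quartiles, Min-Max by visit and dosing method | None, but no grade and no count of subjects |
| Listings 16.2.7.1.1, 16.2.7.1.2 and 16.2.7.1.5 | Each value with limits and low/high mark | None, but no grade |

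A Grade 3-4 result that meets neither of the first two conditions is therefore counted nowhere.

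**Step 2. What PCS adds to the low/high mark**

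The low/high mark is set when a value is below the lower or above the upper limit of normal. PCS is set by the same test, so the two columns always agree. The mock hematology listing illustrates this. Basophils of 2.3% against an upper limit of 2 (2.3/2 = 1.15) and neutrophils of 0.84 against a lower limit of 1.96 (0.84/1.96 = 0.43) both show YES. The listing notes say mock numbers are only examples, so this shows how the rule behaves and is not evidence about the data.

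**Step 3. How often the PCS rule would flag an unaffected subject**

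The plan states no expected flag rate, so there is no figure to reproduce. Inputs:

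- Chemistry: 21 analytes, counted from push SAP 4.3.3.
- Hematology: about 9 (white cell count, a five-part differential by assumption, hemoglobin, hematocrit, platelets). Total m = 21 + 9 = 30.
- Draws: v = 7 for Core HIV-infected subjects (Days 1, 15, 29, 43, 57, 71, 85). Sentinel and Core HIV-uninfected subjects have more.
- Assumption not in the documents: each normal range holds 95% of unaffected values.

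If all values were independent, P(at least one flag) = 1 - 0.95^(m x v):

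- m = 30, one visit: 1 - 0.95^30 = 0.785
- m = 30, seven visits: 1 - 0.95^210 > 0.999
- m = 10, one visit: 1 - 0.95^10 = 0.401
- m = 10, seven visits: 1 - 0.95^70 = 0.972

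Independence is unrealistic for repeated draws in one person. A simulation of 20,000 subjects per setting used latent normal values, with between-analyte correlation of 0, 0.3 or 0.5 and across-visit correlation of 0.5, 0.7 or 0.9. Over seven draws it gave:

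| Analytes | Flagged, lowest to highest | Expected of 20 subjects |
|---|---|---|
| 30 | 81% to 100% | 16.2 to 20.0 |
| 20 | 72% to 99.5% | 14.4 to 19.9 |
| 10 | 54% to 93% | 10.8 to 18.5 |

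The lowest rates come with the strongest correlation (0.5 between analytes, 0.9 across visits).

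**The case against.** The push SAP delivers what Protocol 9.5.2 asks for: by-visit descriptive statistics, change from baseline, and out-of-range flags in listings. No protocol text requires graded laboratory tables. Toxicity oversight during the study does not run through the SAP, since the DMC discusses abnormal laboratory results and receives all Grade 3 and 4 AEs (Protocol 8.8). All of this stands, and it makes the gap one of final reporting, not of subject protection.

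The set of results that escapes a count is also probably small. Protocol 8.3 counts a change as clinically significant if action is required or if the investigator judges it beyond normal physiological fluctuation. Most Grade 3-4 abnormalities are excluded at entry for HIV-infected subjects (Protocol 5.2), so an on-study one will usually be new. This too stands, but small is not zero, and the investigator's judgement still decides.

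With 5 Sentinel and 15 Core subjects, an extreme value would move the displayed minimum or maximum, and the retest rule (push SAP 3.3.2) keeps the original value in the analysis. The result is therefore visible, but it is neither graded nor counted.

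A reader might infer three stronger things that the documents do not support:

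- **That Grade 3-4 results appear in no push table.** Table 14.1.2 and the graded TEAE tables can carry them.
- **That the report will show a PCS count near 100%.** PCS is optional in the text, appears only as a listing column, and has no summary table planned.
- **That push and IM laboratory results must be comparable.** No objective calls for that comparison, and the IM SAP treats the two portions as separate studies. The IM table matters here only as a method the sponsor already uses.

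**Conclusion.** The point holds as a moderate reporting gap in a primary safety objective. PCS, as defined, cannot separate minor from marked abnormalities, and no push laboratory output is graded. Whether a Grade 3-4 laboratory result is counted depends on AE reporting or on a confirmed, related discontinuation.

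The documents give no basis for estimating how many such results would go uncounted. The flag-rate range measures only how poorly the PCS rule discriminates. It rests on the assumed 95% reference ranges, the analyte count and the correlations tried, and it says nothing about missed Grade 3-4 events. Sample size, error rates and the PK bridge are unaffected.

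**What to change.** In push SAP 4.3.3 and its mock outputs:

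1. **Add a table of subjects by worst DAIDS grade per analyte, taken within each dosing method.** The methods are the 15-minute infusion, the 10-, 5- and 1-minute steps, the 30-second push, and follow-up, as they apply to Sentinel, Core HIV-infected and Core HIV-uninfected subjects. Limit it to analytes gradable under Appendix B, which is a separate document and has to be checked for coverage.
2. **Do not copy the programming note under IM Tables 14.3.2.1 and 14.3.2.2.** It picks each subject's highest grade across all visits and periods before counting, which would blur the comparison between dosing methods.
3. **Add a grade column to Listing 16.2.7.1.5**, and keep the out-of-range flags that Protocol 9.5.2 requires.
4. **In both SAPs, define PCS as DAIDS Grade 3 or higher for gradable analytes, or drop the PCS column.**

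The cost is one extra table type and the grading code. The IM tables already need DAIDS grading, so the rules are not new to the study.
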